## 7.0 Identification and Description of Investigational Device

The PillCam® COLON 2 Capsule endoscopy system (manufactured by Given Imaging LTD, Medtronic, Yoqneam, Israel) will be used in this evaluation.

The PillCam® COLON 2 Capsule endoscopy system is comprised of four main subsystems: (1) an ingestible PillCam® COLON 2 capsule; (2) PillCam Recorder; (3) RAPID® software; and (4) Given® Workstation. The PillCam® COLON 2 Capsule endoscopy system includes a new capsule design (PillCam COLON 2), PillCam Recorder (DR3), and a new version of the RAPID® Software (RAPID® 8.3). Modifications were also made to the PillCam® COLON 2 capsule's field of view, effective frame rate, image quality and capsule power management. Changes designed to increase system simplicity and make the management of subjects easier were added as well. For example, the PillCam® COLON 2 includes the RAPID® software which is designed to assess polyp size and an audio-visual guidance system integrated into the PillCam Recorder that is intended to help guide the subject through the procedure. The new PillCam® Endoscopy system with the PillCam® COLON 2 capsule is fully compliant with all safety and radio standards and regulations similar to the currently marketed capsule endoscopy systems.

PillCam® COLON 2 capsule is ingested by the patient after bowel preparation, with a sip of water.

The device does not incorporate any medicinal product, human blood derivative or tissues of animal origin.

### 7.1 PillCam® COLON 2 Capsule

PillCam® COLON 2 has been designed to achieve more complete coverage of the colonic mucosal surfaces. Improvements include:

- Optics with super wide field of view (172 degrees for each imaging head)
- Higher and adaptive frame rate (Up to 35 frames per second)

### 7.2 Given® PillCam Recorder (DR3)

The new generation of PillCam Recorder used in this study has enhanced communication features, computing power, and incorporates a Real Time Viewing screen. These modifications are detailed in the Investigator Brochure.

### 7.3 GIVEN® Workstation

The Workstation is a modified standard personal computer that is intended for reviewing the RAPID® videos generated from the images acquired by the capsule, interpretation and analysis of the acquired data, and for generating reports.

The software program used for video creation and interpretation has several useful features incorporated that aid the physician during the video review.

## 8.0 Study Design

This is a multicenter, prospective, randomized study to evaluate the efficacy of CCE versus CTC in the identification of colonic polyps in a screening population.

Subjects will be enrolled at up to 20 clinical sites in the United States. Subjects who meet the eligibility criteria will be screened by the gastroenterology site for study participation at a baseline visit which will also include a blood test for renal function (eGFR), and will be evaluated on the randomized procedure day (CCE versus CTC) and again on the day of both the blinded and unblinded OC procedures.

Telephone follow-ups will be conducted 5 – 9 days after the CCE/CTC procedure and 5 – 9 days after the unblinded OC procedure to assess subject well-being and capture any AEs, regardless of relationship to the CCE, CTC, or OC procedures. On the second follow-up call after the OC procedure, subjects will be requested to answer procedure preference questions (sample questionnaires are included in Appendix D).

All CCE RAPID® videos and CTC images will be evaluated by local and central readers. All study analyses will be based on central reader results for both CCE and CTC. Two sets of central readers will be utilized, one set for reading of the CCE RAPID® videos and one set for reading the CTC studies. Both groups of readers will be experts in the reading process for their respective procedures. Readers will provide a report of their findings to the sponsor within 2 weeks of capsule ingestion or CTC procedure in order to allow subjects to return within 5 weeks capsule ingestion or CTC procedure to undergo confirmatory OC. The first OC procedure will be performed with the clinician blinded to the CCE or CTC results. Immediately following this blinded procedure, the clinician will review the CCE or CTC results report provided by the sponsor from the central readers, and a second unblinded OC procedure will be performed if there are discrepancies between the CCE/CTC findings and OC.

Colonoscopy must not be performed by the same person who conducts the local CCE reading, or anyone who has reviewed CCE/CTC results for that subject.

In cases of polyp size measurement discrepancies between CCE/CTC and OC, a Clinical Events Committee (CEC) will adjudicate OC polyp size measurements. Bowel preparation regimens for all three procedure types will be standardized across sites and are described in detail in the Appendix.

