
Video/Image Reading
	
All study analyses will be based on central reader results for both CCE and CTC. There will be 2-3 readers for each modality (CCE and CTC). All imaging will be randomly assigned among the readers.
 
OC reports will be generated by the physician performing colonoscopies at the study site.
 
In cases of polyp size measurement discrepancies between CCE/CTC and OC, a Clinical Events Committee (CEC) will adjudicate OC polyp size measurements.

Primary Endpoint
	
The primary endpoint is the diagnostic yield (proportion of subjects shown to have an actionable lesion, defined as any polyp or mass lesion <math>\geq 6</math> mm) by CCE as compared to CTC. Diagnostic yield of CCE/CTC will be calculated in relation to the confirmatory OC results.

Secondary Endpoints
	
The following accuracy measures of CCE versus CTC in the detection of polyps <math>\geq 6</math> mm will be assessed in relation to the confirmatory OC results and expressed on a “per subject” basis (rather than “per polyp”).
 
 
• Negative predictive value (NPV)
 
• Positive predictive value (PPV)
 
• Sensitivity
 
• Specificity
 

Additional Analyses
	
1. [REDACTED]
 
[REDACTED]
 
[REDACTED]
 
[REDACTED]
 
[REDACTED]
 
 
• [REDACTED]
 
• [REDACTED]
 
• [REDACTED]
 
• [REDACTED]
 
 
[REDACTED]
 
[REDACTED]
 
[REDACTED]
 
[REDACTED]
 
[REDACTED]
 
[REDACTED]
 
[REDACTED]
 
[REDACTED]
 
[REDACTED]

	
6. [REDACTED] [REDACTED]
 

• [REDACTED] [REDACTED]

• [REDACTED]

• [REDACTED]

Randomization
	
Subjects will be 1:1 randomized at the gastroenterology study site according to the procedure defined above.

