**8.2 Primary Effectiveness Endpoint**

The primary effectiveness endpoint is the diagnostic yield (proportion of subjects shown to have an actionable lesion, defined as any polyp or mass lesion  $\geq 6$  mm) by capsule colon endoscopy as compared to computed tomographic colonography. Diagnostic yield of CCE and CTC will be calculated in relation to the confirmatory OC results.

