### **8.9 Procedures to Minimize Bias**

A 1:1 randomization will be employed to minimize bias relative to the comparison of the two study arms. In addition, RAPID® videos and CTC images will be randomly distributed among the central readers.

In addition, the confirmatory OC will be conducted first blinded to the CCE/CTC results and then unblinded.

[figure not shown]

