#### **15.0 Data Collection and Processing**

This study will utilize an electronic database and eCRF. All data requested on the eCRF are considered required. Data points not collected and/or recorded will be considered deviations unless otherwise specified.

The Principal Investigator must ensure the accuracy and completeness of the recorded data and then provide his/her signature on the appropriate eCRFs. The Investigator's electronic signature for specific

eCRFs will be documented in compliance with local regulations. Changes to data previously submitted to the sponsor will require a new signature by the Investigator to acknowledge/approve the changes.

Visual and/or computer data review will be performed to identify possible data discrepancies.

In cases of polyp size measurement discrepancies between CCE/CTC and OC, a Clinical Events Committee (CEC) will adjudicate OC polyp size measurements.

Manual and/or automatic queries will be created in the Oracle remote RDC system and will be issued to the site for appropriate response. The site staff will be responsible for resolving all queries in the database.

This study will be using a 21 CFR Part 11 compliant electronic data capture system. All system level validation documentation is retained within the Information Systems group.

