### 21.3 Appendix C3 – OC Procedure Instructions

The confirmatory OC will first be conducted blinded to the CCE/CTC results and then unblinded, if discrepancies in polyp detection are observed, as shown below. For the blinded OC procedure, the colonoscopist will be kept blinded to the CCE or CTC results until the OC procedure visualizes the entire colon. After the blinded colonoscopy, the colonoscopist will review the RAPID or CTC report with the CCE or CTC results. If results are not congruent, a second colonoscopy will be performed.

For both the blinded and unblinded OC studies:

- Study GI endoscopists (not the same GI physician that performs the local reading) will be trained by the sponsor on polyp size estimation using study designated biopsy forceps (Radial Jaw 4, by Boston Scientific), to confirm homogeneous methods between all participating study centers.
- The OC examination will be recorded electronically and sent to the sponsor. Only the subject study ID and initials should appear in the recorded video either by inserting the initials to the recording machine or by including a snapshot of the subject's initials written on a piece of paper at the beginning of the procedure. The withdrawal time will need to be at least 6 minutes as per common practice.
- Size measurement for every polyp using the reference forceps will be documented in a picture (i.e., open study forceps will be placed as close as possible to the polyp, on maximum linear dimension, while it is being photographed).
- All OC still pictures will be saved in a digital format (.tif or .bmp). Quality copies of the pictures taken during OC will be provided to the study sponsor with the OC report.
- These videos and pictures will be archived by the sponsor and may be used in future analyses to, for example, provide further information about observed lesions, to assess study quality, or add further information regarding comparisons between colonoscopy and capsule findings.

For each OC procedure the following information will be collected:

- Adequacy of colon preparation for each colorectal segment (cecum, ascending, transverse, descending/sigmoid, and rectum) and for the overall colon using a validated system, as shown in Appendix C4. This information should be recorded in the CRF.
- Colonoscopy report
- The following information will be collected and documented for each polyp detected:
  - Location: Colon segment (i.e., cecum, ascending, transverse, descending/sigmoid, and rectum)

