### 23.0 Appendix E – Matching Algorithm

To address inherent uncertainties in the comparison of polyp localizations and sizes, a polyp-matching algorithm will be used to determine the agreement between CCE/CTC and OC. The first step of this procedure is to identify all polyps  $\geq 6$ mm detected by any method (OC, CCE, or CTC). The polyp with the largest estimated diameter of either OC or CCE/CTC will be referred to as the ‘reference’ polyp. The colon segment location (cecum, ascending, transverse, descending/sigmoid, or rectum) of the reference polyp will be determined and recorded. The largest polyp identified using the other method within the same or an immediately adjacent segment location of the “reference” polyp will be used to determine agreement based on a size matching algorithm. If there were two polyps of equal size that were “the largest” and located in different segments of the colon, then the location and size matching algorithm will be repeated for each of these reference polyps to determine agreement of CCE/CTC with OC.

For a given polyp to be considered a match between CCE/CTC and OC, it has to be assessed within 50% (plus or minus) of the size of the largest estimate of the two studies (CCE and OC or CTC and OC) and must appear within the same or immediately adjacent colon segments.

For example, if CCE detected a 10 mm polyp, the  $\pm 50\%$  range would be 5-15 mm. If colonoscopy detected a 6 mm polyp ( $\pm 50\%$  range = 3-9mm) in the same or immediately adjacent segment, the 2 polyps would be considered a match (CCE true positive) because the two ranges overlap.

The “reference” polyp size will then be used to assign the polyp to the following groups:  $\geq 6$  mm, and/or  $\geq 10$  mm in size. For each subject, the CCE/CTC evaluation will be classified into one of four categories of agreement relative to OC, as shown in Table 3.

Table 3. Polyp Matching Accuracy Assessment

Findings of CCE or CTC	Findings of blinded or unblinded colonoscopy	
	Positive	Negative

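### OC polyp sizes are reopened only where they disagree with CCE/CTC, so the test under evaluation selects which reference values are revised; size and direction of the effect cannot be fixed from the documents

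*Combined protocol and SAP*

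**What the plan says.** The same rule stands in three places. Section 8.0 reads "In cases of polyp size measurement discrepancies between CCE/CTC and OC, a Clinical Events Committee (CEC) will adjudicate OC polyp size measurements". The Synopsis (4.0, image-reading row) and section 15.0 repeat that the committee "will adjudicate OC polyp size measurements". Section 8.11 makes the central readers' CCE and CTC findings final, so the index-test size is never revised.

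The OC size matters because "Diagnostic yield of CCE and CTC will be calculated in relation to the confirmatory OC results" (8.2), and the secondary accuracy measures use the same reference (8.3). Appendix E builds agreement from sizes. On the reference polyp it says "The polyp with the largest estimated diameter of either OC or CCE/CTC will be referred to as the" reference, and for a match "it has to be assessed within 50% (plus or minus) of the size of the largest estimate of the two studies".

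CCE polyps are sized with the capsule software's estimation utility (Appendix A4). CTC is analysed by central readers on 3D software (Appendix B4). For OC, "Size measurement for every polyp using the reference forceps will be documented in a picture" (Appendix C3).

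The bias controls in 8.9 are randomization, random allocation of cases to readers, and that "the confirmatory OC will be conducted first blinded to the CCE/CTC results and then unblinded". The committee is not mentioned there. No visible text defines a discrepancy, masks the committee to arm or to the CCE/CTC size, or says whether the site size or the adjudicated size enters Appendix E. The planned sensitivity analyses in Appendix E vary the matching size and use OC as reference; none that is visible uses un-adjudicated OC sizes.

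**The concern.** A reference standard should be set without regard to the test it judges. Here the index result decides which OC sizes get a second look. A pair that disagrees by chance can be moved into agreement; a pair that agrees by chance cannot be moved out of it. More pairs are reopened in an arm with noisier or biased sizing, and because the two arms use different sizing tools, randomization does not balance this. At stake are the match status, the Table 3 cells and through them the CCE-CTC comparison of yield, sensitivity, specificity and predictive values. This follows from the stated trigger. How much it matters depends on details that the documents leave open.

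**Working it through.** **1. The plan's own figure.** Section 9.1 gives yields of 25% (CCE) and 15% (CTC), a 5-point margin, 10% attrition and more than 80% power. With n per arm = (z₁₋α + z₀.₈)² × [p₁(1−p₁) + p₀(1−p₀)] / (p₁ − p₀ + δ)²:

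- One-sided 5%: (1.645 + 0.842)² × (0.1875 + 0.1275) / 0.15² = 86.6, so 87; 87/0.9 gives 97.
- One-sided 2.5%: 110; 110/0.9 gives 123.

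The planned 160 per arm exceeds both. Simulating the 98%/96% rule with four looks and an assumed Beta(1,1) prior gives 95.5% power at 160 per arm and 93.7% at 144. The stated power is reproduced. The question is what feeds the yields.

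**2. Does the trigger alone raise agreement?** Let m be the match rate on first measurement and r the chance that a non-matching pair matches on a second, independent and unbiased OC measurement. Reviewing non-matches only gives m + (1−m)r, which cannot be below m. Re-measuring every polyp gives m again. Simulation with one polyp per subject, the strict 50% rule, assumed gamma true sizes and OC error CV 25%:

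| Assumed test error CV, bias | Site sizes | All re-measured | Non-matches only | Implied r |
|---|---|---|---|---|
| 25%, 1.0 | 95.4% | 95.3% | 99.2% | 3.78/4.62 = 0.82 |
| 40%, 1.0 | 86.9% | 86.9% | 94.3% | 7.46/13.14 = 0.57 |
| 25%, 1.3 | 88.9% | 88.9% | 96.4% | 7.45/11.08 = 0.67 |
| 40%, 1.3 | 82.7% | 82.7% | 91.3% | 8.58/17.28 = 0.50 |

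So selection alone raises agreement, and more where the test is noisier or biased. Appendix E true positives rise by 1.7, 3.3, 4.7 and 5.2 points of polyp-bearing subjects. If the trigger is instead disagreement across 6 mm, matching still rises, but true positives change by −2.9 to +0.1 points, because the reference size is the larger of the two. The unstated trigger therefore decides even the sign.

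**3. Two readings of the match rule.** Read strictly, the smaller size must be at least half the larger, a ratio up to 2:1. The worked example in Appendix E instead justifies a match by overlap of the two ±50% ranges: 1.5s ≥ 0.5L, a ratio up to 3:1. Its own sizes, 10 and 6 mm, match either way; 10 and 4 mm match only by overlap (2–6 against 5–15).

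**4. Effect on a comparison of two tests.** All inputs are assumed: 62% of subjects with a polyp; lognormal size, median 5.7 mm, log-SD 0.5; detection 88% by the index test and 95% by OC; sizing error 35% in one arm and 20% in the other, 25% for site OC, 12% for the committee. Sensitivity gap, less noisy minus noisier arm, strict matching:

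| OC size used | Gap (points) |
|---|---|
| Masked committee, all polyps | about 3.5 |
| Masked, discrepant only, non-match or combined trigger | 1.9–2.4 |
| Masked, discrepant only, 6 mm-category trigger | 3.7 |
| Discrepant only, pulled halfway to the index size | gone (88.9% vs 88.7%) |

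Site sizes give 87.9 − 83.2 = 4.7. Separate codings of the same assumptions differ: masked review of all polyps ranges from 3.1 to 4.0, and masked review under the combined trigger from 2.2 to 2.7. Under the overlap reading the gap is within about 0.5 point for every option (0.6 in one coding). The noisier arm is adjudicated more often, 27% against 20% of pairs.

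Relative to masked sizing of all polyps, selection alone moves the yield difference about 0.1 to 0.3 point toward the noisier test under strict matching (0.4 in one coding).

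**5. Against the margin.** With CCE truly 5 points lower, the rule in 9.2 with the assumed flat prior claims non-inferiority in 6.5–6.8% of simulated trials. A 1-point gain in the CCE arm only raises this to 9.2–10.3%, a slope of 2.6 to 3.5 per point. By linear interpolation, 0.1 to 0.3 point adds 0.1 × 2.6 = 0.3 to 0.3 × 3.5 = 1.05 percentage points. A 1-point gain in the CTC arm only lowers the rate to 4.2–4.6%. An equal 2-point gain in both arms leaves it at 6.6–6.8%.

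**The case against.** A reader might infer that the rule erases a real accuracy difference between CCE and CTC. The documents do not support that. In step 4 the gap vanishes under strict matching only when an unmasked committee is assumed to move toward the index size, and nothing says that it sees that size. Under the overlap reading there is hardly a gap to erase.

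A reader might also infer that the rule favours the sponsor's device. It is worded identically for both arms, and no sizing error or discrepancy rate is given for either test, so the favoured arm is unknown.

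Nor does OC size alone settle 6 mm status: Table 3 classifies a matched polyp by the larger of the two sizes, so a 7 mm index polyp matched to a 5 mm OC polyp is already a true positive.

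Three further points weigh in the plan's favour. Forceps photographs go to the sponsor and are archived, blinded and unblinded OC findings are on separate forms, and nothing says that site sizes are overwritten. Appendix E already plans sensitivity analyses. Some additional analyses are redacted (4.0, 8.4, 9.3), so one on un-adjudicated sizes may exist, and a committee charter may specify masking.

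These points limit the magnitude. They do not remove the selective trigger, which masking alone would leave in place. If adjudicated sizes replace site sizes, the OC-as-reference analysis inherits the problem.

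**Conclusion.** The point holds as a flaw in a stated rule: the index test selects which reference sizes are reopened, only the reference can move, and agreeing pairs go unchecked. This tends to raise size agreement, possibly by different amounts in the two arms. The consequence for yield and accuracy is probably modest. Under the assumed 35% against 20% sizing error and strict matching, a masked committee narrows a gap of about 3.5 points to about 2 under a non-match or combined trigger, leaves it un-narrowed under a 6 mm trigger, and moves the yield difference by about 0.1 to 0.3 point against a 5-point margin. Under overlap matching the sensitivity gap is negligible whichever OC sizes are used. These figures illustrate the mechanism and are not estimates for this trial. Sizing error by arm, the trigger, masking and the matching reading are all unstated. The point is worth correcting because the correction is cheap, not because the primary conclusion is shown to be at risk.

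**What to change.** - In the Synopsis, 8.0 and 15.0, state that the committee sizes OC polyps from the existing forceps photographs, masked to arm and to the CCE/CTC size, and define the discrepancy that triggers review.
- Keep the original site OC sizes. In Appendix E, say which size enters matching, and pre-specify primary yield and the accuracy measures on un-adjudicated sizes as a sensitivity analysis, with adjudication rates reported by arm.
- Reconcile the match rule in Appendix E with its worked example, since the size of this effect depends on the reading.
- Preferably, have the committee size every photographed polyp that either method calls 6 mm or larger, not only discrepant ones. This addresses the selective trigger itself; masking alone does not.

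The cost is protocol and charter wording, one repeat analysis and, for the wider set, modest extra work for an existing committee. No new procedures or subjects are needed.

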### 8.1 Study Objective

The primary objective of this multicenter, prospective, randomized study is to assess the diagnostic yield of CCE versus CTC in a screening population.

**8.2 Primary Effectiveness Endpoint**

The primary effectiveness endpoint is the diagnostic yield (proportion of subjects shown to have an actionable lesion, defined as any polyp or mass lesion  $\geq 6$  mm) by capsule colon endoscopy as compared to computed tomographic colonography. Diagnostic yield of CCE and CTC will be calculated in relation to the confirmatory OC results.

**8.3 Secondary Effectiveness Endpoints**

The following accuracy measures of CCE versus CTC in the detection of polyps  $\geq 6$  mm will be assessed in relation to the confirmatory OC results and expressed on a “per subject” basis (rather than “per polyp”).

- Negative predictive value (NPV)
- Positive predictive value (PPV)
- Sensitivity
- Specificity

